Basis for Calculating the Number of Acquired Images	
The data for agreement, sensitivity and specificity can be summarized as in the table below. For agreement, the terms agree and disagree are with respect to each other. For sensitivity and specificity, the terms agree and disagree are with respect to truth. So for sensitivity, truth is tumor and for specificity truth is not tumor.
 
Agreement Table
 

	cC	

FS Results	Agree	DisAgree		

Agree	b	a+b	

Disagree	c	d	c+d	

	a+c	b+d	nT	

 
The estimate of agreement is <math>p_{AG} = (a+d)/n_T</math>. It is desired to test the hypothesis that the agreement is greater than 80%. This is compatible with the expected result that both the sensitivity and the specificity will be about 90%. Thus the hypothesis to be tested is:
 $H_0: \pi_{AG} = 80\% \text{ vs } H_A: \pi_{AG} > 80\%$ 
Where <math>\pi_{AG}</math> is the percent agreement between Frozen Section and cCeLL. This will be tested utilizing the exact binomial test. Estimates of agreement from the pilot study indicate that the agreement will be greater than 86%. In this study, there will be 250 subjects available for analysis for the estimation and testing of agreement. For outcome results, if the agreement is 86%, with the sample size of 250, the probability the estimated agreement will be greater than 80% is greater than 90%.
			cC		FS Results	Agree	DisAgree		Agree	b	a+b	Disagree	c	d	c+d		a+c	b+d	n T
		cC																		
FS Results	Agree	DisAgree																		
	Agree	b	a+b																	
Disagree	c	d	c+d																	
	a+c	b+d	n T																	

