### **8.3 Statistical Analysis and Interpretation**

#### **8.3.1 Methods and Sample Size**

The data for agreement, sensitivity and specificity can be summarized as in the table below. For agreement, the terms agree and disagree are with respect to each other. For sensitivity and specificity, the terms agree and disagree are with respect to truth. So for sensitivity, truth is tumor and for specificity truth is not tumor. It should also be noted that since the total sample size was chosen to be 250, no power calculations were done; however, a probability calculation that the estimated parameter is greater than the null hypothesis was presented.

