**Agreement Table**

		cC		
FS Results	Agree	DisAgree		
	a	b	a+b	
Disagree	c	d	c+d	
		a+c	b+d	n T

The estimate of agreement is  $p_{AG} = (a+d)/n_T$ . It is desired to test the hypothesis that the agreement is greater than 80%. This is compatible with the expected result that both the sensitivity and the specificity will be about 90%. Thus the hypothesis to be tested is that the agreement is 80% (H0: Null hypothesis) versus the alternative hypothesis that the agreement is greater than 80% (HA: Alternative hypothesis).

$$H_0: \pi_{AG} = 80\% \text{ vs } H_A: \pi_{AG} > 80\%$$

Where  $\pi_{AG}$  is the percent agreement between Frozen Section and cCell. This will be tested utilizing the exact binomial test. Estimates of agreement from the pilot study indicate that the agreement will be greater than 86%. In this study, there will be 250 participants available for analysis for the estimation and testing of agreement. For outcome results, if the agreement is 86%, with the sample size of 250, the probability the estimated agreement will be greater than 80% is greater than 90%. That is,  $P(p_{AG} > 80\%) > 90\%$ .

**Sensitivity Table** – Sensitivity is only calculated when the truth standard is positive for tumor.

Agreement Table with Tumor Truth

		cC		
FS Results	Agree w/Truth	Disagree w/Truth		
	e	f	e+f	
Disagree	g	h	g+h	
		e+g	f+h	n T

The sensitivity of the Frozen Section is given by  $p_{SenF} = (e+f)/n_T$  and the sensitivity of cCell is given by  $p_{SenC} = (e+g)/n_T$ . It is desired to demonstrate that the sensitivity of cCell is non inferior to that of Frozen section.

The non inferiority of the sensitivity of cCell result versus the sensitivity of the Frozen Section is given as:

$$H_0: \pi_{SenF} - \pi_{SenC} > \Delta \text{ versus } H_A: \pi_{SenF} - \pi_{SenC} \leq \Delta$$

Here  $\pi_{SenF}$  is the true sensitivity for Frozen Section and  $\pi_{SenC}$  is the true sensitivity for cCell. The parameter  $\Delta$  is the non-inferiority limit. In this study, it is proposed to utilize a  $\Delta=0.05$  (5%). If that  $\Delta$  is used and the anticipated sensitivity for both Frozen Section and cCell is 90%, then

with a sample size of 200 tumor positive samples the probability the difference between the estimated sensitivities is less than 5% is greater than 90%. That is  $P((\pi_{\text{SenF}} - \pi_{\text{SenC}} \leq 5\%) > 90\%.$

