**Specificity Table** – Specificity is only calculated when the truth standard is negative for tumor.

Agreement Table with Non-Tumor Truth

		cC		
FS Results	Agree w/Truth	Disagree w/Truth		
Agree	r	s	r+s	
Disagree	t	u	t+u	
		r+t	s+u	$n_2$

The specificity of the Frozen Section is given by  $p_{\text{SpeF}} = (r+d)/n_2$  and the specificity of cCeLL is given by  $p_{\text{SpeC}} = (r+d)/n_2$ . It is desired to demonstrate that the specificity of cCeLL is non-inferior to that of Frozen section.

The non-inferiority of the specificity of cCell result versus the specificity of the Frozen Section is given as:

$$H_0: \pi_{\text{SpeCF}} - \pi_{\text{SpeC}} > \Delta \text{ versus } H_A: \pi_{\text{SpeF}} - \pi_{\text{SpeC}} \leq \Delta$$

Here  $\pi_{\text{SpeF}}$  is the true specificity for Frozen Section and  $\pi_{\text{SpeC}}$  is the true specificity for cCell. The parameter  $\Delta$  is the non-inferiority limit. In this study, it is proposed to utilize a  $\Delta=0.10$  (10%). If that  $\Delta$  is used and the anticipated specificity for both Frozen Section and cCell is 90%, then with a sample size of 50 tumor negative samples the probability the difference between the estimated specificities is less than 10% is greater than 80%. That is  $P(\pi_{\text{SpeF}} - \pi_{\text{SpeC}} \leq 10\%) > 80\%.$

The sensitivity and the specificity hypotheses will be tested using McNemar's test by constructing an upper 97.5% confidence bound for the difference between the two methods. If the upper bound is less than  $\Delta$  (5% for sensitivity and 10% for specificity) then the two images are said to be non-inferior. The upper confidence bound is given by:

$$p_{\text{FS}} - p_{\text{cC}} + z_{0.05} \text{se}(p_{\text{FS}} - p_{\text{cC}}), \text{ where}$$

$$\text{se}(p_{\text{FS}} - p_{\text{cC}}) = \frac{\sqrt{(b+c)}}{n}$$

The standard error (se) for the difference depends on the number of discordant pairs (a and b). Where a and b correspond to f and g from the sensitivity table and to t and s from the specificity table. The estimates  $p_{\text{FS}}$  and  $p_{\text{cC}}$  correspond to the sensitivity of the Frozen Section,

$p_{\text{SenF}}$ , and the sensitivity of cCell,  $p_{\text{SenC}}$  when sensitivity is being tested and they correspond to the specificity of the Frozen Section,  $p_{\text{SenF}}$ , and the specificity of cCell,  $p_{\text{SenC}}$ , when specificity is being tested.

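### The sample sizes rest on the chance that a point estimate clears a limit, which is well above the chance of meeting the decision rules in Section 8.3.1

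*Combined protocol and SAP*

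**What the plan says.** The Synopsis, under Basis for Calculating the Number of Acquired Images, justifies 250 samples by saying that at 86% agreement "the probability the estimated agreement will be greater than 80% is greater than 90" per cent. Section 8.3.1 repeats this and gives two parallel statements:

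- Sensitivity, 200 tumor samples, margin 5%: "the probability the difference between the estimated sensitivities is less than 5% is greater than 90" per cent.
- Specificity, 50 normal samples, margin 10%: "the probability the difference between the estimated specificities is less than 10% is greater than 80" per cent.

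Section 8.3.1 opens by saying that the total of 250 was chosen and that "no power calculations were done; however, a probability calculation that the estimated parameter is greater than the null hypothesis was presented". The Synopsis has no such sentence.

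The decision rules are set out separately in Section 8.3.1. On agreement it says "This will be tested utilizing the exact binomial test", against a null of 80%, with no alpha. Sensitivity and specificity are judged by whether an upper confidence bound for frozen section minus cCeLL lies below the margin. The text calls this a 97.5% bound, but the formula uses z_0.05. The standard error is the square root of the number of discordant pairs divided by n.

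**The concern.** An estimate on the right side of a limit is a weaker event than a significant test or a bound inside a margin. A reader of the Synopsis sees a probability above 90% offered as the reason for the sample size and will naturally take it as the chance of success. If the real chance for the non-inferiority tests is near even when the two methods are equally accurate, the sponsor and ethics boards should know that before the data are seen.

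The presentation also has three defects:

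- Section 8.3.1 writes the two non-inferiority probabilities with π, which it defines as the true values, although the sentences concern estimates.
- The Synopsis prints the sensitivity statement with the difference greater than 5%, the reverse of Section 8.3.1.
- The Synopsis gives no probability for specificity.

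**Working it through.** **Inputs from Section 8.3.1.** Agreement: null 80%, planned 86%, n = 250. Sensitivity: 90% for both methods, n = 200, margin 0.05. Specificity: 90% for both, n = 50, margin 0.10. The true difference is therefore 0.

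**Inputs not given.** Alpha for agreement: 2.5% and 5% one-sided are both shown. z for the bound: 1.96 (the words) and 1.645 (the formula) are both shown. Discordance between the methods: two scenarios are used.

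- A: 14% in both tissue groups, from 1 − 0.86.
- B: independent errors. Agreement is 0.9 × 0.9 + 0.1 × 0.1 = 82%, so discordance is 18%.

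Samples are treated as independent.

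**Step 1. Reproduce the plan's figures.** Agreement: P(X > 200) for X binomial(250, 0.86) is 99.4%. For the paired differences, the number of discordant pairs K is binomial(n, discordance), and given K the direction of each is binomial with probability 1/2. Then:

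- P(estimated sensitivity difference < 5%) = 96.4% at 14% discordance, 94.4% at 18%, and 93.4% at 20%, the maximum possible with 90%/90%.
- P(estimated specificity difference < 10%) = 95.6%, 93.4% and 92.4%.

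The statements of more than 90%, 90% and 80% all hold at the plan's values.

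**Step 2. Chance of passing the agreement test.** One-sided 2.5% needs at least 213 of 250 (actual level 2.12%). One-sided 5% needs at least 211 (actual level 4.53%).

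**Step 3. Chance of passing non-inferiority.** With f and g the two discordant cells, the rule is (f − g)/n + z·√(f + g)/n < Δ, summed exactly over all (f, g).

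| Test | Plan's figure | A: 14% discordance, 86% agreement | B: 18% discordance, 82% agreement |
|---|---|---|---|
| Agreement, one-sided 2.5% / 5% | >90% | 68% / 80% | 11% / 18% |
| Sensitivity, z = 1.96 / 1.645 | >90% | 49% / 60% | 39% / 51% |
| Specificity, z = 1.96 / 1.645 | >80% | 52% / 62% | 43% / 53% |

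**Step 4. What would give 90% for sensitivity?** At 4% discordance the chance is 92% with z = 1.96. At 5% it is 87% with z = 1.96 and 93% with z = 1.645. So discordance must be about 4–5%. With exactly 86% agreement, 35 of 250 samples are discordant. At 90% specificity for both methods, at most 10 of the 50 normals can be discordant (5 errors each, none shared). That leaves at least 25 of 200 tumor samples (12.5%), where the chance is 54% or 64%.

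**Step 5. The sensitivity bound at an observed difference of 0.**

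- 28 of 200 discordant (14%): 1.96 × √28 / 200 = 5.19%, which fails; 1.645 × √28 / 200 = 4.35%, which passes.
- 25 of 200 discordant (12.5%): 1.96 × √25 / 200 = 4.90%, which passes.
- Largest passing count: (0.05 × 200 / 1.96)² = 26.03, so 26 pairs; with 1.645 it is 36.96, so 36 pairs.

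**The case against.** The best defence is that the plan is candid. Section 8.3.1 says power was not computed and names what was computed instead, and the figures are right for that quantity. This stands: there is no miscalculation. But the caveat is missing from the Synopsis, and nowhere is the reader told the chance of passing.

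Second, 86% may be a floor: "Estimates of agreement from the pilot study indicate that the agreement will be greater than 86" per cent. At 12% discordance the sensitivity chance rises only to 55.5% (z = 1.96) or 65.5% (z = 1.645), so this narrows the gap without closing it.

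Third, the plan never assumes independent errors. This also stands. With 90%/90% the agreement can lie anywhere from 80% to 100%, so 86% is compatible with the accuracy assumptions. A reader might infer that the planning values contradict each other because independence gives 82%. They do not; the dependence is simply unstated, and scenario B is a sensitivity case.

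A reader might also infer that results exactly as planned would fail non-inferiority for sensitivity. The documents do not support that. The 5.19% bound needs both z = 1.96 and an assumed 14% discordance among tumor samples. The printed z_0.05 gives a pass, and so does 12.5% discordance with z = 1.96.

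**Conclusion.** The point holds as a gap between the stated basis for the sample size and the decision rules. In scenario A the chances of passing are 68–80% for agreement, 49–60% for sensitivity and 52–62% for specificity, against stated figures of more than 90%, 90% and 80%. In scenario B they are 11–18%, 39–51% and 43–53%. Each range spans the two readings of alpha or z. The two scenarios must not be mixed in one statement, because they imply different agreement.

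The conclusion on the two non-inferiority tests does not depend on which z is meant. It rests on equal 90% accuracy, the assumed discordance and independent samples. Section 6.2 allows up to three samples per participant, and clustering is not modelled here.

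A reader might want one overall chance of success. The plan names three primary endpoints but does not say that all three must pass, so a joint figure has no stated rule behind it.

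**What to change.** 1. Reconcile the 97.5% wording with z_0.05 in Section 8.3.1, and state the alpha for the agreement test. The two-sided 95% interval in the Synopsis under Analysis Methods should be brought into line with the choice.
2. In the Synopsis and Section 8.3.1, report the chance of meeting the actual decision rule for each endpoint. Use one coherent discordance scenario at a time, with the scenario stated. Note that samples are treated as independent although a participant may contribute up to three.
3. Carry the Section 8.3.1 caveat that no power calculation was done into the Synopsis.
4. Write any estimate-based probability that is kept with p instead of π.
5. Correct the direction of the sensitivity statement in the Synopsis.
6. Give a joint probability only if the plan first states that all three tests must pass.

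The cost is wording and a short calculation. No samples are added, but the figures shown will be less favourable.

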	
Sensitivity Table – This is only tabulated when the truth standard is positive for tumor.
 
Agreement Table with Tumor Truth
 
  
 	cC		
 
 FS Results	Agree w/Truth	DisAgree w/Truth		
   
 Agree	e	F	e+f	
 
 Disagree	g	H	g+h	
 
 	e+g	f+h	n1	
  
 
The sensitivity of the Frozen Section is given by <math>p_{SenF} = (e+f)/n_1</math> and the sensitivity of cCeLL is given by <math>p_{SenC} = (e+g)/n_1</math>. It is desired to demonstrate that the sensitivity of cCeLL is non inferior to that of Frozen section.
 
The non inferiority of the sensitivity of cCeLL result versus the sensitivity of the Frozen Section is given as:
 $H_0: \pi_{SenF} - \pi_{SenC} > \Delta \text{ versus } H_A: \pi_{SenF} - \pi_{SenC} \leq \Delta$ 
Here <math>\pi_{SenF}</math> is the true sensitivity for Frozen Section and <math>\pi_{SenC}</math> is the true sensitivity for cCell. Where <math>\Delta</math> is the non inferiority limit. In this study, it is proposed to utilize a <math>\Delta=0.05</math> (5%). If that <math>\Delta</math> is used and the anticipated sensitivity is 90%, then with a sample size of 200 tumor positive samples the probability the difference between the estimated sensitivities is greater than 5% is greater than 90%.
			cC		FS Results	Agree w/Truth	DisAgree w/Truth		Agree	e	F	e+f	Disagree	g	H	g+h		e+g	f+h	n 1
		cC																			
FS Results	Agree w/Truth	DisAgree w/Truth																			
Agree	e	F	e+f																		
Disagree	g	H	g+h																		
	e+g	f+h	n 1																		

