Analysis Methods	
Primary Endpoints
 
Comparison of the sensitivity/specificity of cCeLL-Ex vivo reading results, and the sensitivity/specificity of the frozen section reading results in one pathological inquiry for brain tumor tissue
 

• Sensitivity of cCeLL-Ex vivo reading result in 1 patient in pathological inquiry for brain tumor tissue: Probability that PS is positive if CC-H positive

• Specificity of cCeLL-Ex vivo reading result in 1 patient in pathological inquiry for brain tumor tissue: Probability that PS is negative if CC-H is negative

• Sensitivity of frozen section reading results for brain tumor tissue: Probability that FS is positive if PS is positive

• Specificity of frozen section reading results from brain tumor tissue: Probability that PS is negative if FS is negative

 
The ratio of the clinical sensitivity/specificity of a cCeLL Ex-vivo image and the sensitivity/specificity of the frozen section image of 1 patient in the pathological inquiry for the total reading results is presented, respectively. To identify a 95 % bilateral confidence interval for the difference between cCeLL- Ex vivo and the frozen section sensitivity/specificity.
 
The statistical significance of the difference between cCeLL-Ex vivo and the frozen section sensitivity/specificity ratio is tested by the McNemar test.
 
Secondary Endpoints
 

1. Comparison of cCeLL-Ex vivo imaging and reading time with frozen section reading time

i. The cCeLL-Ex vivo imaging time is measured and recorded in minutes from the time the fluorescent dye is applied to the specimen for image acquisition

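### Section 8.3.1 sets a 97.5% upper bound for non-inferiority, but its formula uses `z_0.05`, which read as an upper-tail quantile gives only a 95% bound

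*Combined protocol and SAP*

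**What the plan says.** Section 8.3.1 tests both hypotheses "by constructing an upper 97.5% confidence bound for the difference between the two methods". The rule is: "If the upper bound is less than $\Delta$ (5% for sensitivity and 10% for specificity) then the two images are said to be non-inferior". The bound is then written as p_FS − p_cC + `z_0.05` × se, with se = √(b+c)/n. The subscript convention is not defined.

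The Synopsis (Analysis Methods, Primary Endpoints) describes the same comparison differently: "To identify a 95 % bilateral confidence interval for the difference", and the significance of the "sensitivity/specificity ratio is tested by the McNemar test".

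Four further statements bear on the same rule:

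- The specificity formulas in section 8.3.1 are both (r+d)/n2, one for frozen section and one for cCeLL. The specificity table has cells r, s, t and u.
- The standard error uses b+c, but the sentence below it names the discordant pairs as a and b.
- On sensitivity planning, the Synopsis says "the probability the difference between the estimated sensitivities is greater than 5% is greater than 90"%.
- On the same point, section 8.3.1 says "the probability the difference between the estimated sensitivities is less than 5% is greater than 90"%.

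**The concern.** The words and the formula give different confidence levels for the quantity that decides two primary endpoints. A programmer who codes the formula with the upper 5% point runs each test at a nominal one-sided 5%. One who follows the words runs it at 2.5%.

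Nothing else in the plan settles the matter. Section 8.3.1 reports no power calculation, and its probability statements concern point estimates, so they do not involve z. A multiplier that can be settled after the data are seen allows a borderline verdict to be chosen.

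The neighbouring slips touch the same rule. Two identical specificity expressions have a difference of zero whatever the data, and a McNemar test of a difference does not use the 5% or 10% margin.

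**Working it through.** **Level of the bound.** The upper 5% point of the normal distribution is 1.645, which gives an upper 95% bound. The upper 2.5% point is 1.960, which gives an upper 97.5% bound. Taking `z_0.05` as the two-sided 5% critical value also gives 1.960. So the stated 97.5% is reproduced on the two-sided reading and not on the upper-tail reading.

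**Rule applied.** Let f be the pairs in which only frozen section is right and g the pairs in which only cCeLL is right (s and t for specificity). Non-inferiority is declared if (f−g)/n + z√(f+g)/n < Δ. From the plan: n = 200 and Δ = 5% for sensitivity; n = 50 and Δ = 10% for specificity. The splits below are illustrations. The plan gives no discordance within the tumour or normal group; its 86% agreement refers to all 250 samples.

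| Case | n | Split | Bound, 1.960 | Bound, 1.645 |
|---|---|---|---|---|
| Sensitivity, 86% agreement, 90% v 90% | 200 | 14/14 | 5.19% fails | 4.35% passes |
| Sensitivity, 87% agreement, equal | 200 | 13/13 | 4.997% passes | 4.19% passes |
| Sensitivity, 181/200 v 179/200 | 200 | 11/9 | 5.38% fails | 4.68% passes |
| Sensitivity, independent errors | 200 | 18/18 | 5.88% fails | 4.93% passes |
| Specificity, 45/50 v 44/50 | 50 | 3/2 | 10.77% fails | 9.36% passes |
| Specificity, equal | 50 | 3/3 | 9.60% passes | 8.06% passes |

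For the 11/9 row: 2/200 + 1.960 × √20/200 = 0.0100 + 0.0438 = 0.0538; with 1.645, 0.0100 + 0.0368 = 0.0468. For the 3/2 row: 1/50 + 1.960 × √5/50 = 0.0200 + 0.0877 = 0.1077; with 1.645, 0.0200 + 0.0736 = 0.0936. The 36 pairs under independent errors come from 200 × 2 × 0.9 × 0.1.

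At 14% discordance or less, 14 sensitivity splits change verdict, of which only 14/14 has zero observed difference. One specificity split changes, 3/2.

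**How often the readings disagree.** Exact enumeration with zero true difference and independent samples; discordant count Binomial(n, d), each pair equally likely to favour either method:

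| Discordance d | 5% | 8% | 10% | 12% | 14% | 18% |
|---|---|---|---|---|---|---|
| Sensitivity, n = 200 | 6.0% | 9.0% | 9.5% | 10.1% | 10.9% | 12.1% |
| Specificity, n = 50 | 2.1% | 5.9% | 7.7% | 8.7% | 9.1% | 9.6% |

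**Actual one-sided error when the true difference equals the margin** (1.960 v 1.645):

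- Sensitivity: 3.4% v 6.1% at 10% discordance; 3.2% v 5.5% at 14%.
- Specificity: 11.2% v 11.2% at 10%; 7.8% v 8.7% at 12%; 5.9% v 7.8% at 14%.

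**The specificity formulas taken literally.** Suppose frozen section is right in 45/50 and cCeLL in 39/50, with s = 6 and t = 0. The printed expressions give 0 + 1.960 × √6/50 = 9.6%, which passes. With (r+s)/n2 and (r+t)/n2 the bound is 12.0% + 9.6% = 21.6%, which fails.

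**The case against.** The best defence is that the level is stated twice in words. The 97.5% bound and the two-sided 95% interval agree with each other, and `z_0.05` as shorthand for the two-sided 5% critical value fits both. On that view the fault is one of notation, and choosing 1.645 later would contradict two explicit statements. This is a fair account of what was probably meant. But the plan does not say so, and the printed formula is what would be coded.

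The gain for specificity is also limited. At n = 50 the actual error exceeds 2.5% with either multiplier, and at 10% discordance the two are identical. That stands: the correction makes the rule definite but does not bring specificity to its nominal level.

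The (r+d) formulas are evident misprints. The table margins r+s and r+t, and the parallel sensitivity formulas, show what was intended, so an analyst would be unlikely to report the 9.6%. The illustration shows only that the printed text cannot be used.

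The Synopsis does not rest on the McNemar test alone, since it also asks for an interval, and section 8.3.1 attaches the McNemar name to its own bound. The correction therefore has to cover both places. The greater-than-5% slip concerns a planning probability and does not affect the decision rule.

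**Conclusion.** The concern holds. As printed, section 8.3.1 contradicts itself on the confidence level that decides two primary endpoints: 97.5% in words, 95% in the formula on its natural reading. The nominal one-sided level is 2.5% or 5%. For sensitivity the actual error at the margin is 3.2% v 5.5% at 14% discordance.

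Most results would not depend on the choice. With zero true difference and 5% to 14% discordance, the readings agree in 89.1% to 94.0% of sensitivity analyses and 90.9% to 97.9% of specificity analyses. The rest include unremarkable results such as an 11 to 9 split.

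These figures rest on assumed discordance and on independent samples, although section 6.2 allows up to three samples per participant. The contradiction itself rests on neither assumption. Because it sits in a primary decision rule and is cheap to remove, it must be corrected before the data are analysed.

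**What to change.** In section 8.3.1, write `z_0.025` = 1.96 in the bound. In the Synopsis, name this bound, compared with 5% for sensitivity and 10% for specificity, as the single non-inferiority test in place of the McNemar test of a difference, and describe it in the same way in section 8.3.1.

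In the same edit:

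- Write specificity as (r+s)/n2 for frozen section and (r+t)/n2 for cCeLL.
- Call the discordant cells b and c throughout, matching f and g for sensitivity and s and t for specificity.
- In the Synopsis sensitivity statement, change greater than 5% to less than 5%.
- While the section is open, replace the sensitivity symbols used for specificity in its closing sentence, and the stray SpeCF subscript in the specificity null hypothesis.

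The cost is text edits only, with no added samples. Compared with 1.645, the chance of declaring non-inferiority at zero true difference falls by 6.0 to 10.9 percentage points for sensitivity and 2.1 to 9.1 for specificity at 5% to 14% discordance. That is the price of the level the plan already states in words.

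### The specificity bound in 8.3.1 is labelled 97.5% but carries a one-sided error of about 3-6% at 14-30% discordance, not 2.5%, and its printed multiplier conflicts with the label

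*Combined protocol and SAP*

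**What the plan says.** Sensitivity and specificity, each compared between cCeLL and frozen section, are among the primary endpoints (section 8.1). Section 8.3.1 tests both for non-inferiority by "constructing an upper 97.5% confidence bound for the difference between the two methods". The bound is the frozen-section estimate minus the cCeLL estimate, plus z_0.05 times a standard error of √(b+c)/n. The text explains that "The standard error (se) for the difference depends on the number of discordant pairs".

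The decision rule begins "If the upper bound is less than" the margin, and the margins are "5% for sensitivity and 10% for specificity". For specificity the plan works "with a sample size of 50 tumor negative samples"; for sensitivity, "with a sample size of 200 tumor positive samples".

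Section 8.3.1 also says that no power calculation was made. The synopsis (Analysis Methods) asks for a two-sided 95% interval for the same differences and a McNemar test. No section gives an exact or score method, a continuity correction or a small-sample check for the bound.

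**The concern.** The standard error is built only from the discordant pairs that happen to be observed. With 50 normal samples and 10-18% discordance, only 5 to 9 such pairs are expected. When chance produces few of them, the difference looks small and the standard error shrinks as well, so the bound falls below the margin too easily. A bound described as 97.5% should let a device that is exactly 10 points worse pass 2.5% of the time. If it passes more often, a primary conclusion rests on weaker evidence than the plan states.

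The printed multiplier is a second problem. The usual reading of z_0.05 is 1.645, which makes a nominal 95% bound, whereas the label requires 1.96.

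**Working it through.** **Inputs.** From 8.3.1: n = 50, margin Δ = 0.10, and the bound as printed. For sensitivity: n = 200, Δ = 0.05. The multiplier is taken first as 1.96 (the 97.5% label, which matches the synopsis's two-sided 95% interval) and then as 1.645 (the printed subscript).

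**Assumption.** Discordance on normal tissue is not given, so it is varied from 10% to 30%:
- 10% is the smallest value possible with a 10-point deficit.
- 14% and 20% match the 86% and 80% agreement figures in 8.3.1, which are pooled over tumor and normal samples.
- 18% is what independent errors give with both methods at 90%: 2 × 0.9 × 0.1.
- 26% is what independent errors give with frozen section at 90% and cCeLL at 80%: 0.9 × 0.2 + 0.1 × 0.8.

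**The plan's own figure first.** The plan states that "the probability the difference between the estimated specificities is less than 10% is greater than 80" percent. With both specificities at 90% and independent errors (18% discordance), enumeration gives 93.4%, so the statement is true. It concerns the point estimate, however. The chance that the upper bound itself clears 10% in that setting is 43% (z = 1.96).

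**Method.** Let s be the pairs with frozen section right and cCeLL wrong, and t the reverse. Sum the trinomial probabilities of every (s, t) for which (s − t)/n + z√(s + t)/n < Δ. For the error rate, set P(s) − P(t) = Δ; for the chance of passing when the methods are equal, set P(s) = P(t).

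**Hand check at 10% discordance.** Here P(t) = 0. With t = 0 and z = 1.96, the bound is 0, 5.9%, 9.5% and 12.8% for s = 0, 1, 2 and 3, so the rule passes when s ≤ 2. P(s ≤ 2 | n = 50, p = 0.10) = 0.9^50 + 50(0.1)(0.9^49) + 1225(0.1²)(0.9^48) = 0.0052 + 0.0286 + 0.0779 = 11.2%.

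**Comparator.** The paired score (Tango) test passes when (s − t − nΔ)/√(n[2q + Δ(1 − Δ)]) ≤ −1.96, where q is the estimate of P(t) restricted to the margin. For s = 2, t = 0, q = 0 and the statistic is (2 − 5)/√(50 × 0.09) = −1.41, a fail. The corresponding score bound is 13.5%, against 9.5% from the planned formula, so the choice of bound alone reverses the conclusion on those data.

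**Specificity, n = 50, margin 10%:**

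| Discordance | Error, z = 1.96 | Error, z = 1.645 | Error, score | Pass if equal, z = 1.96 | Pass if equal, score |
|---|---|---|---|---|---|
| 10% | 11.2% | 11.2% | 0.5% | 65% | 44% |
| 12% | 7.8% | 8.7% | 1.2% | 58% | 41% |
| 14% | 5.9% | 7.8% | 1.5% | 52% | 39% |
| 18% | 4.5% | 6.8% | 2.1% | 43% | 34% |
| 20% | 4.2% | 6.5% | 2.2% | 39% | 32% |
| 26% | 3.5% | 6.0% | 2.4% | 31% | 26% |
| 30% | 3.1% | 6.0% | 2.4% | 26% | 24% |

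The usual paired Wald standard error gives essentially the same error rates. Over a wider grid (10-70% discordance) the planned bound with z = 1.96 never fell below 2.6%, and the score bound never exceeded 2.6%.

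**Sensitivity, n = 200, margin 5%, z = 1.96:** the error is 3.4%, 3.2% and 2.9% at 10, 14 and 18% discordance, and 6.2% in the limiting case of 5%.

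**The case against.** The strongest reply has four parts.

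- **The 11% figure is a corner.** A reader might infer that specificity would be passed wrongly about 4-11% of the time, or up to four times as often as stated. The documents do not support that as a general range. At 10% discordance one discordant cell has probability zero, and the value also depends on n being exactly 50: it is 4.4% at n = 47, 12.9% at n = 48 and 5.3% at n = 60. Section 8.3.2 takes every sample analyzable by frozen section, so the final n is not fixed. A range that stops at 20% discordance also leaves out the independent-errors case at the margin (26%). This objection stands, and the conclusion is framed accordingly.
- **The score bound costs success and is conservative at low discordance.** Its error is 0.5% at 10% discordance, and a single cCeLL miss with none the other way already fails (statistic −1.89). This stands as a cost. But part of the planned rule's higher success comes from exceeding its stated error rate, and the plan states no power for this test that the change would break.
- **Sensitivity is hardly affected.** This stands. At 10-18% discordance the excess is under one percentage point, so a reader should not infer a comparable problem there.
- **The zero-width bound looks alarming but decides nothing.** With no discordant pairs the score bound is 7.1%, which also passes at 10%.

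None of this restores the 2.5% error at n = 50, and no other section supplies a different method.

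**Conclusion.** The point holds for specificity. With z = 1.96, the planned bound has an exact one-sided error of about 3-6% at 14-30% discordance, against the 2.5% its label implies; 11.2% is a limiting case only. With the printed z_0.05 read as 1.645, the error is about 6-11%. Correcting the multiplier to 1.96 is needed but does not remove the excess.

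These figures rest on an assumed discordance for normal tissue, on n = 50, and on independent samples, although section 5.4 allows several samples per participant. They are also rates at the margin: a true deficit greater than 10 points passes less often. The matter should be settled before analysis because it affects a primary decision and takes one formula to correct.

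**What to change.** In section 8.3.1, replace the specificity bound with the paired-proportion score (Tango) one-sided 97.5% upper bound for frozen section minus cCeLL, and declare non-inferiority if it is below 10%. The margin stays as it is. Reconcile the multiplier with the 97.5% label wherever the present formula is kept. Using the score bound for sensitivity as well is optional, for consistency.

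The cost is one formula; the method is in standard software and needs no new data. The real price is a lower chance of passing specificity when the methods are truly equal: 65% to 44% at 10% discordance, 52% to 39% at 14%, 43% to 34% at 18% and 31% to 26% at 26%. For sensitivity the fall would be about 2-7 points at 10-18% discordance. If the sponsor finds the specificity figures too low, the remedies are more normal samples or an openly stated different level. The change does not address clustering of samples within participants.
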